#### Statistical Principles

##### Confidence intervals and P values

Confidence intervals and P values will be based on 0.05 as significance level. Adjustments for multiple comparisons will be implemented where appropriate but not for pre-defined study endpoints.

Where applicable, normally distributed continuous outcomes will be presented as mean with 95% CI or standard deviations. Continuous outcomes that are not normally distributed will be transformed using

a suitable transformation before reporting 95% CIs. Where a suitable transformation cannot be found, medians will be presented with interquartile ranges. For discrete (or count) data we will find interquartile ranges. Binary data will be presented as counts and proportions.

#### Population pharmacokinetic/pharmacodynamic modelling

Population pharmacokinetic/pharmacodynamic modelling will be performed in line with best practice (Byon et al CPT Pharmacometrics Syst Pharmacol. 2013 Jul 3;2(7):e51.). Internal evaluation of the developed model will be performed using standard goodness-of-fit plots, prediction-corrected visual predictive checks and absence of parameter correlation. Parameter imprecision will be assessed using the covariance step in NONMEM or the sampling importance resampling procedure as implemented in Perl Speaks NONMEM. Nested models will be compared using the objective function, that follows approximately a chi-square distribution. Non-nested models will be compared using the Akaike Information Criterion. Covariates will be included based on 1) physiological plausibility and 2) statistical significance as assessed by the objective function value and 3) improvement of goodness-of-fit plots. From the final model, individual empirical bayes estimates for traditional pharmacokinetic endpoints like the area under the concentration time curve (AUC), maximum concentration (Cmax), time of maximum concentration (Tmax) and elimination half-life (T½) will be obtained.

#### Adherence and protocol deviations

Missing data will not be imputed due to the small number of participants in each group. Participants who miss an appointment date will be retained in the study and available data will be analysed. If human errors are made during TB31F administration, the actual administered dose and time will be used in analyses.

A best-worst case sensitivity analysis may be performed. Lack of precision is expected in some outcome measures, for instance estimates of (low) transmission reducing activity (TRA) by SMFA. For some analyses, we may thus use TRA estimates that are inferred from antibody concentration based on the best fit model for the association between antibody concentration and TRA. Details are provided on page 16.

#### Multiple comparisons

Primary outcomes are numerous and often related (e.g. TRA and TBA are closely related). We will account for the risk of false-discovery by recalculating p-values using permutation tests. As part of this approach, we will generate an empirical distribution from study data, automatically adjusting p-values for the complexity and dependence structure in the data. This obviates the need for traditional multiple testing correction amongst the primary aims. Secondary outcomes are hypothesis-generating, and therefore, not adjustments for multiple comparisons will be applied.

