## Objectives

### Cohort 1: Safety

#### Primary objectives

- To assess the reactogenicity, tolerability, and safety of increasing doses of mAb TB31F in adults and school-age children
- To assess the population pharmacokinetics (pK) of a single subcutaneous injection of mAb TB31F in Malian adults and school-age children

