### Cohort 2: Efficacy

#### Primary efficacy objective

- To assess the transmission-blocking activity of mAb TB31F in serum as assessed in the Direct Membrane Feeding Assay (DMFA) at each dose level in naturally *P. falciparum* infected individuals

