#### Primary safety/pharmacokinetics objectives

- To assess the reactogenicity, tolerability, and safety of increasing doses of mAb TB31F in Malian individuals
- To assess the population pharmacokinetics (PK) of a single sub-cutaneous injection of mAb TB31F in Malian individuals

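### The SAP drops traditional multiplicity correction for the primary aims because p-values come from permutation, but specifies no joint procedure, and another section gives pre-defined endpoints no adjustment

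*SAP*

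**What the plan says.** The Multiple comparisons section opens with the premise "Primary outcomes are numerous and often related (e.g. TRA and TBA are closely related"). It continues: "We will account for the risk of false-discovery by recalculating p-values using permutation tests". An empirical distribution is to be generated from the study data, "automatically adjusting p-values for the complexity and dependence structure in the data", and the conclusion drawn is "This obviates the need for traditional multiple testing correction amongst the primary aims". Secondary outcomes are left unadjusted as hypothesis-generating.

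A little earlier, Confidence intervals and P values sets the significance level at 0.05 and adds: "Adjustments for multiple comparisons will be implemented where appropriate but not for pre-defined study endpoints".

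On what is primary, the Cohort 2 efficacy objective is transmission-blocking activity "as assessed in the Direct Membrane Feeding Assay (DMFA) at each dose level in naturally" infected individuals. Safety and pharmacokinetics are also primary, in Cohort 1 ("To assess the reactogenicity, tolerability, and safety of increasing doses of mAb TB31F in adults and school-age children") and in Cohort 2 ("To assess the reactogenicity, tolerability, and safety of increasing doses of mAb TB31F in Malian individuals"). The outcome list does not label outcomes as primary or secondary; it refers to protocol section 2, which was not available for this review. Outcome 8, the within-individual reduction in infected mosquitoes by DMFA at day 5, appears to be the primary efficacy outcome.

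**The concern.** The waiver rests on a property that permutation does not have by itself. Replacing a model-based reference distribution with a permutation distribution protects a single test against wrong distributional assumptions. It does nothing about the number of tests unless the permuted quantity is itself joint, such as the largest statistic or smallest p-value across the family, or unless the resulting p-values are then corrected.

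The text does not say that either is done, so a report could claim protection across the primary aims that was never delivered. The two sections on multiplicity also state different rules for the same endpoints: one analyst could report unadjusted primary p-values and another adjusted ones, each citing the SAP.

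**Working it through.** **What a reader would need, and what is stated.**

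- *Joint statistic or follow-on correction:* none named in Multiple comparisons. The model descriptions under Analyses in relation to endpoints give model-based estimates and confidence intervals and mention no permutation step.
- *Family of tests:* described only as numerous; no list or count.
- *Permutation unit:* not stated (arm labels, day labels or other).
- *Error rate and level:* false discovery is mentioned loosely. The 0.05 level is given for p-values generally, not for a family.

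**The two rules side by side.** Confidence intervals and P values excludes pre-defined endpoints from adjustment. Multiple comparisons says the p-values for primary outcomes are adjusted. Primary outcomes are pre-defined, so both rules apply to them and they disagree as worded.

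**The example.** TRA does not appear among the primary objectives of either cohort. TRA by SMFA is a secondary efficacy objective, and the section on outcomes related to transmission reducing activity calls SMFA exploratory. The pair offered as related primary outcomes is therefore not a pair of primary outcomes.

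**Mechanism check.** The SAP gives no multiplicity figure to reproduce. As an illustration only, null data were simulated with 15 controls against 30 treated (the 1:2 layout of Table 3), two uncorrelated normal endpoints, 499 permutations, 2,000 trials and two-sided 0.05. A single permutation test rejected in 4.75% of trials. At least one of the two separate permutation tests rejected in 9.3%, close to the theoretical 1 − 0.95² = 9.75%. A joint max-T permutation test rejected in 5.15%. At a correlation of 0.95 the last two figures were 5.6% and 4.2%. The joint step supplies the control, not the permutation. These endpoints are artificial, so the figures do not measure this trial's error.

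**Size for the apparent primary efficacy outcome.** Inputs: two dose levels in Cohort 2 (expected about 30 mg, and 100 mg; Table 3), different participants at each, and a one-tailed 0.025 test (Sample size). Treating the two within-group tests as independent:

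- both nulls true: 1 − 0.975² = 1 − 0.950625 = 4.94%, against 2.5% for one test;
- one null true: 2.5%;
- both nulls true, each at 0.0125 (Bonferroni, or Holm's first step): 1 − 0.9875² = 2.48%.

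**Power cost of Holm.** A mixed logistic simulation (2,000 trials per scenario; true reduction 90% against a bound of 80%; 40 mosquitoes per timepoint; ICC read on the latent scale, an assumption) compared one-sided 0.025 with 0.0125. Power fell from about 98% to 96% (30 participants, 15% baseline, ICC 0.5; the SAP states 97%) and from about 95% to 91% (20 participants, 20% baseline, ICC 0.4; the SAP states 91.5%). That is a loss of roughly 2 and 4 points. The Wald test was slightly liberal (3.2% at nominal 2.5%), and a smaller simulation of the first scenario (200 runs) gave 94.5% or 96% at 0.025, depending on how the 80% bound was placed. Only the rounded differences should be used.

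**The case against.** The best defence is that this is under-specification rather than error. The text waives only traditional correction and says that p-values are adjusted for dependence. Test-by-test permutation ignores dependence between tests, so a joint procedure may well be what the authors have in mind. That stands as far as intent goes. A reader might infer that the primary p-values will certainly go without control across tests; the SAP does not support that. What remains is that correction is waived in favour of a procedure that cannot be identified from the text.

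A reader might also infer that permutation cannot address outcome 8, because arm labels say nothing about a within-group change. The SAP never says that arm labels are permuted. Day labels could be swapped within participants to test no change from baseline, although that would not directly test the 80% bound used in Sample size. The supportable criticism is that the permutation unit is unstated.

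Nor do the documents support an inflation figure for between-arm tests or for a large family. Between-arm DMFA comparisons appear in outcomes 10 and 12, which correspond to secondary objectives and are openly left unadjusted. Between-group safety comparisons are largely optional. Test counts and correlations are not given.

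The two sections can be partly reconciled by reading the earlier one as referring to traditional corrections only, but it does not say so. Finally, whether two doses in a Phase 1/2a trial need joint control is a matter of judgement, and leaving them unadjusted is defensible if no familywise protection is claimed.

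**Conclusion.** The point holds as a defect of specification and consistency that should be corrected. The SAP draws a conclusion (no traditional correction needed) that follows only if a joint procedure or a follow-on correction is used, and states neither. Its two multiplicity rules conflict as worded, and its example of related primary outcomes does not match its primary objectives.

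The demonstrable size is moderate: 4.9% instead of 2.5% for outcome 8 across two doses. This assumes that outcome 8 is the primary efficacy outcome, that each dose is tested one-sided at 0.025 without adjustment, that the tests are independent, and that both nulls hold (each true reduction exactly at the tested bound). No figure is claimed for any other family.

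**What to change.** 1. In Multiple comparisons, delete or qualify the sentence that dismisses traditional correction. State either that primary p-values are joint step-down max-T or min-P permutation p-values at a named error rate and level, with the family listed, or that no control across tests is claimed. For any between-arm primary test, permute whole participants within the randomisation structure: dose group and, in Cohort 2, block.
2. For outcome 8 at the two doses, state either Holm or separate unadjusted tests per dose with no familywise claim. Name a test that matches the within-participant hypothesis, including whether the null is no change or the 80% bound.
3. Make Confidence intervals and P values and Multiple comparisons state the same rule, and replace the TRA/TBA example with outcomes that are primary.

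The cost is SAP wording and a few lines of code. Jointly adjusted p-values will be somewhat larger. Holm would cost roughly 2 to 4 points of power at its first step (one-sided 0.0125), under the assumed latent-scale ICC. Testing the doses separately costs no power.

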## Study Outcome Measures

### Outcome Definitions

(Protocol section 2).

#### Safety outcome measures:

1. Occurrence of at least possibly related
  - a) solicited local and systemic adverse events (AEs) within 7 days of mAb TB31F administration
  - b) unsolicited AEs within 28 days of mAb TB31F administration
  - c) serious adverse events during the entire study period

#### Pharmacokinetic/pharmacodynamic outcome measures:

2. Terminal serum half-life ( $t_{1/2}$ )
3. Maximum observed serum concentration (Cmax)
4. Time to reach maximum serum concentration (tmax)
5. Accumulation index (Racc), and area under the serum concentration-time curve (AUC0- $\tau$ , AUC0- $t$  and AUC)
6. The impact of the potential covariates total serum IgG, serum leptin, total protein, albumin, and pre-albumin as surrogates for malnutrition and protein metabolism, as well as age, weight, height, and nutritional status on the TB31F pharmacokinetics.
7. The parameter estimates for the fixed and random effects, as well as their imprecision, describing the integral model for the pharmacokinetics and pharmacodynamics of TB31F in adults and children.

A large number of efficacy outcome measures are listed in the protocol (section 2). These outcome measures are related in terms of the endpoints (oocyst prevalence, oocyst density, proportion infectious individuals) and comparisons (within group, between group, between assays) are grouped as such.

#### Efficacy outcome measures related to within-group % reduction in proportion infected mosquitoes:

8. Group averaged within-individual percent reduction in the proportion of mosquitoes infected at day 5 post-treatment relative to baseline (day 0), assessed through direct membrane feeding assays (DMFA) and measured as oocyst prevalence (timeframe: day 0 [baseline] & 5)
9. Group averaged within-individual percent reduction in the proportion of mosquitoes infected in DSF, at all feeding timepoints relative to baseline (day 0). Comparisons of these reductions between groups at each post-baseline timepoint and comparisons of the reductions between post-baseline timepoints for each group (timeframe: day 0 [baseline], 1, and 5)
10. Group averaged within-individual percent reduction in the proportion of mosquitoes infected in DMFA, at all feeding timepoints relative to baseline (day 0). Comparisons of these reductions between groups at each post-baseline timepoint and comparisons of the reductions between post-baseline timepoints for each group (timeframe: day 0 [baseline], 1, 5, and 14)

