## Introduction

TB31F-Mali (full title 'A Phase 1/2a single centre, randomised, placebo-controlled, double-blind, dose escalation, age de-escalation, study to evaluate the safety, tolerability, pharmacokinetics, and *Plasmodium falciparum* transmission-reducing activity of monoclonal antibody TB31F in malaria-exposed Malian adults and children') is a Phase 1/2a single-centre, randomised, double-blind trial that aims to assess the safety and tolerability of monoclonal antibody (mAb) TB31F in Malian adults and school-age children, assess the pharmacokinetics of mAb TB31F in Malian adults and school-age children and assess the *P. falciparum* transmission reducing activity (TRA) of TB31F in naturally *P. falciparum* infected Malian individuals.

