## Method

### Study design

The study is designed as a Phase 1/2a single-centre, double-blind, dose escalation, age de-escalation trial in malaria-exposed Malian adults and children. Two sequential stages of clinical research are conducted, each recruiting a distinct cohort of participants to confirm: 1. TB31F safety and 2. TB31F efficacy. Pharmacokinetic measurements will be performed in both safety and efficacy cohorts.

In total, a minimum of 165 participants will be recruited and enrolled; 45 adults and 30 children for the safety study, and ≥ 90 adults and children for the efficacy study. In the tables below, the cohorts are described with the number of participants, the duration of follow-up and the dose of TB31F administered.

*Table 1. Study design for Cohort 1 (Adults): Safety and pharmacokinetics (18-50 years of age)*

Group	Dose	N	Volume TB31F/Saline	Sample timepoints*	Safety follow-up after each dose administration
1	1A: Control (normal saline)	5	0.2 mL	Day 0 (Baseline), 1, 5, 7, 14, 21, 28, 42, 56, 84	Solicited local and systemic AEs (days 1-7); Unsolicited AEs (study duration); SAEs (study duration)
	1B: 10 mg mAb TB31F	10			
2	2A: Control (normal saline)	5	2 mL		
	2B: 100 mg mAb TB31F	10			
3	3A: Control (normal saline)	5	4 mL		
	3B: 200 mg mAb TB31F	10			

\* Group 1 participants will be followed-up until day 28

*Table 2. Study design for Cohort 1 (Children): Safety and pharmacokinetics in school age children (>10-15 years)*

Group	Dose	N	Volume TB31F/Saline	Sample timepoints	Safety follow-up after each dose administration
4	4A: Control (normal saline)	5	0.2 mL	Day 0 (Baseline), 1, 5, 7, 14, 21, 28, 42, 56, 84	Solicited local and systemic AEs (days 1-7); Unsolicited AEs (study duration); SAEs (study duration)
	4B: 10 mg mAb TB31F	10			
5	5A: Control (normal saline)	5	2.0 mL		
	5B: 100 mg mAb TB31F	10			

*Table 3. Study design for Cohort 2: Efficacy in a mixed age cohort (>10-50 years of age)*

Group	Dose	N	Volume TB31F/Saline	Sample timepoints	Safety follow-up after each dose administration
6.1	6AB: Control (normal saline)	15	0.6* mL	Day 0 (Baseline), 1, 5, 14, 21, 28, 56, 84	Solicited local and systemic AEs (days 1-7); Unsolicited AEs (study duration); SAEs (study duration)
	6B: 30 mg mAb TB31F	30	0.6* mL		
6.2	6AC: Control (normal saline)	15	2.0 mL		
	6C: 100 mg mAb TB31F	30	2.0 mL		

AE = Adverse events, SAE = Serious adverse events. Participants will be randomised in a 1:2:1:2 ratio to the 6AB, 6B, 6AC, or 6C group.

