### Efficacy outcome measures

#### **Efficacy outcome measures related to within-group % reduction in proportion infected mosquitoes:**

We will determine averaged within-individual percent reduction in the proportion of mosquitoes infected at days post-treatment (1, 5, 14) compared to baseline (day 0) for each group. This will be assessed through DMFA and DSF and outcomes for these different feeding assays will be presented separately as percentage reduction (with 100% as total reduction of transmission, and negative values as enhanced transmission) with 95% confidence interval. Data will be analysed for all individuals who received the product per protocol and only for those individuals who are infectious at baseline (i.e. infecting at least one mosquito with any number of oocysts). All analyses on within-individual percentage reduction in the proportion of infected mosquitoes will use a mixed effects generalized linear model assuming a binomial error structure and a log-link, using individual mosquito data with day of follow-up and dose of TB31F and their interaction as fixed effects. A random intercept will be added to models to allow for participant-level variation in pre-intervention transmissibility and thus account for the correlation between outcomes for mosquito samples from the same participant (i.e. intra-cluster correlation).

In exploratory analyses, these analyses will be performed following stratification for naturally acquired transmission reducing immunity, as quantified by SMFA at baseline (pre-TB31F administration) samples.

The impact of naturally acquired transmission reducing immunity, assessed in baseline samples by SMFA (TRA>50%; TRA>80%) and by antibody prevalence to known gamete antigens Pfs230 and Pfs48/45, on infecting mosquitoes will also be determined. For this, TRA as categorical variable and antibody prevalence (binary variable), will be added as fixed effects to mixed effects logistic regression models on proportion infected mosquitoes at baseline (pre-TB31F administration). These models may be expanded to include human genetic factors (e.g. a fixed effect for HbAS or HbAC carriage as compared to wild-type HbAA).

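### Outcome 8, apparently the primary efficacy outcome, is a change from baseline within each group, so natural change in infectivity by day 5 is mixed with the TB31F effect

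*SAP*

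**What the plan says.** The SAP Introduction gives the trial's title as "randomised, placebo-controlled, double-blind, dose escalation, age de-escalation". In Cohort 2, Table 3 under Study design has two saline groups of 15 and two TB31F groups of 30, and its note says "Participants will be randomised in a 1:2:1:2 ratio to the 6AB, 6B, 6AC, or 6C group".

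The primary efficacy objective is transmission-blocking activity "as assessed in the Direct Membrane Feeding Assay (DMFA) at each dose level in naturally *P. falciparum* infected individuals". It names no comparator. Under Study Outcome Measures, outcome 8 is the "Group averaged within-individual percent reduction in the proportion of mosquitoes infected at day 5 post-treatment relative to baseline (day 0", by DMFA, under a heading about within-group reduction. Outcomes 9 and 10 share that heading, but each adds "Comparisons of these reductions between groups at each post-baseline timepoint and comparisons of the reductions between post-baseline timepoints for each group". Outcome 8 has no such clause.

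The matching text under Analysis Methods reports the reduction "compared to baseline (day 0) for each group". It fits a log-link binomial mixed model "using individual mosquito data with day of follow-up and dose of TB31F and their interaction as fixed effects", and names no contrast against saline as the efficacy estimate.

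Sample size gives three power figures (97%, 91.5% and 96%) for showing a reduction above 80% when the true reduction is 90%, one-sided at 0.025. It states no assumption about a control arm.

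**The concern.** A before-after change within a treated group measures the drug effect only if infectivity would otherwise have stayed the same from day 0 to day 5. The SAP neither states nor supports that assumption. Thirty participants are randomised to saline in Cohort 2, and they supply the comparison that would remove the need for it.

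As written, the measure that answers the primary objective and the >80% target that sized the trial are both set against baseline. The controlled comparisons of the same data sit in other outcomes. The Multiple comparisons section treats secondary outcomes as hypothesis-generating, so a controlled contrast placed there would carry less weight than the uncontrolled estimate.

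**Working it through.** **1. Which test do the stated powers describe?** Inputs from Sample size: null reduction 80%, true reduction 90%, one-sided 0.025, 40 mosquitoes per participant per timepoint. The three scenarios are: 30 participants, 15% baseline, ICC 0.5; 20 analysed, 20%, 0.4; and 30 participants, 30%, 0.8.

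The simulation used a random-intercept logistic model, as the Sample size text describes, with a Wald test. ICC was read on the latent scale: variance = ICC/(1-ICC) × π²/3, which gives 3.29, 2.19 and 13.16. The reduction was taken on the proportion for the average participant. There were 1,000 runs for each one-arm figure.

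| Scenario | SAP | One-arm, day 5 v day 0 |
|---|---|---|
| 1 | 97% | 97.5% |
| 2 | 91.5% | 93.5% |
| 3 | 96% | 97.7% |

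All three agree within 2 points. No version with a control arm matched all three, or the 97%. For scenario 1 with 30 v 30, a comparison at day 5 only gave 47-79%, and a difference in change gave 83-93%, depending on how ICC and reduction were read. The target was therefore, in effect, powered as a one-arm change from baseline.

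**2. What the before-after figure estimates.** Let E be the reduction relative to saline and d the fall in saline infectivity from day 0 to day 5 (negative for a rise). Then

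before-after reduction = 1 - (1-d)(1-E).

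With E = 80%:
- d = 0: 1 - 1.0 × 0.2 = 80%
- d = 10%: 1 - 0.9 × 0.2 = 82%
- d = 20%: 1 - 0.8 × 0.2 = 84%
- d = 30%: 1 - 0.7 × 0.2 = 86%
- d = 50%: 1 - 0.5 × 0.2 = 90%
- 20% rise: 1 - 1.2 × 0.2 = 76%

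With E = 0 the apparent reduction is d itself. Read the other way, an observed 80% corresponds to 1 - 0.2/(1-d) against saline: 78%, 71% and 60% for d = 10%, 30% and 50%.

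**3. Chance of concluding >80% when E is exactly 80%** (scenario 1 inputs, nominal 2.5%; d is an assumption, since the SAP gives none).

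| Saline fall | Before-after test | Saline-adjusted test, 30 v 30 |
|---|---|---|
| 0 | about 2% | 1.5% |
| 10% | 9% | 1.5% |
| 20% | 26-29% | 2.0% |
| 30% | 60-63% | 2.0% |
| 50% | 97-98% | 2.5% |

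Ranges span two sets of runs; the 10% row comes from one. The last column rests on 400 runs per row; a smaller set of 250 runs gave about 3-6%. Simulation error is up to about 2 points.

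**4. A rise instead of a fall.** With E = 90% and a 20% rise, the before-after figure is 1 - 1.2 × 0.1 = 88%, and power falls to about 84%.

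**5. Power of the saline-adjusted contrast** (null 80%, true 90%, scenario 1): about 92-93% with 30 pooled saline and about 82-83% with 15. Against a null of no effect it is about 100% with either.

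**The case against.** The strongest reply is that the saline group is far from ignored, and that is correct. Outcome 10 compares the same DMFA reductions between groups, day 5 included. Outcomes 12, 15 and 18 compare DMFA prevalence, oocyst density and participant infectivity between groups at each feeding timepoint. The reduction is also to be reported for each group, saline included, so a fall under saline would be visible beside the TB31F figure. A reader might infer that the plan has no placebo-controlled efficacy analysis; the SAP does not support that. What remains is which contrast leads.

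Three other stronger readings also fail:

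- **That outcome 8 is declared primary.** The SAP does not label it. Outcome Definitions points to section 2 of the protocol, which is not at hand, and Multiple comparisons calls the primary outcomes numerous. The status is inferred from the primary objective and from outcome 8 being the single-timepoint DMFA measure.
- **That >80% is a formal success rule.** The test against 80% appears only under Sample size. The analysis text plans estimates with 95% confidence intervals. The rates in the working describe a rule implied by the power calculation.
- **That the bias must favour TB31F.** The SAP does not say which way infectivity moves over five days.

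Restricting one analysis to participants infectious at day 0 might also look like a large source of bias. Through mosquito sampling alone it adds only about 1-2% in a beta-binomial calculation at the SAP's inputs, and everyone treated per protocol is analysed as well.

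**Conclusion.** The point holds as one about the leading estimate. Outcome 8 and the >80% power basis are set against baseline, so the estimate equals efficacy against saline only if infectivity would not otherwise change by day 5. The bias is nil when d = 0. At E = 80% it is 4 to 10 percentage points for falls of 20% to 50%, enough to push the chance of a wrong >80% conclusion from about 2% to between about a quarter and nearly all trials. A rise would understate TB31F.

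This rests on outcome 8 being primary, on an assumed range for d, and on the SAP's baseline and ICC. The simulated model has a logit link, whereas the planned model for this outcome has a log link. For the saline-adjusted test, the 80% threshold was converted to the logit scale using the assumed fall; under a log link it would be fixed at log 0.2. The exact percentages are therefore indicative. The bias formula does not depend on the link.

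**What to change.** In outcome 8 and in the matching analysis text, define the leading estimate for each dose as

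1 - (day-5/day-0 ratio under TB31F) / (day-5/day-0 ratio under saline),

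taken from the day-by-dose interaction already in the model. Keep the within-arm reduction as supportive.

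State whether saline groups 6AB and 6AC are pooled. They differ in volume (0.6 and 2.0 mL). The Randomization section describes allocation within each dose group, while the note to Table 3 gives a single four-way ratio, so the basis for pooling needs to be explicit. Then restate the power for the controlled contrast, and say whether >80% is a decision rule or only a planning target.

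No new data or model is needed, but Sample size must be revised as well as the outcome wording. At a true 90%, power to show >80% falls from about 97% to about 92-93% with 30 pooled saline, or to about 82-83% with the 15 volume-matched saline. It would be lower if response varies between participants. In a cruder calculation (ratio with jackknife standard error, not the planned model), a participant SD of 0.5 in log reduction gave 65% before-after and 50% saline-adjusted.
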